### Recruitment at Affiliate Facilities:

Recruitment may also occur at affiliate facilities (hospitals or rehabilitation facilities). Clinicians at these facilities will hand recruitment cards to inpatient Veterans with stroke on their units and the Veterans' caregivers. The cards will contain information about the study and a contact number. We will also post recruitment flyers with the research nurse's contact information at these facilities. If interested, the caregiver or Veteran will contact study staff who will arrange a time to explain the study, screen for eligibility and consent

either in-person at the facility or over the phone. All other recruitment and enrollment procedures will be followed as outlined above. Affiliate facility staff members will not be directly engaged in research and no patient information will be shared from the affiliate facility.

**Recruitment tracking:** We will track the number of caregivers who decline to participate and the reasons for their non-participation.

## **Randomization:**

The proposed study will use a two-group randomized design with 3 assessment points (baseline, approximately 11 weeks, and approximately 19 weeks). Following baseline assessments, the participant will be randomly assigned to one of the two study groups (Intervention or Usual Care). The Pocock-Simon covariate adaptive randomization procedure will be used so that there will be approximately equal number of subjects assigned to the two groups within each covariate level (depressed or not and high or low ADL) and within each study site. The statistician will develop the randomization scheme and share it with the project coordinator and a research staff member at each site. When a caregiver is enrolled in the study, this staff member at site will obtain the group assignment for that caregiver from the randomization system.

## **Data Collection:**

Research personnel will follow a step-by-step study procedure manual to collect the data. Research staff will meet or telephone caregivers who are interested in learning more about the study. We will arrange times to meet or talk with the caregivers that are convenient with the caregivers. The research staff will discuss the study and provide the caregivers a copy of the informed consent document, so that they can review it and/or discuss with their family and friends. For caregivers who are willing to participate, the research staff will arrange an in-person or telephone meeting to determine the caregivers' study eligibility (also see inclusion/exclusion criteria & recruitment and enrollment sections). For eligible caregivers, the research staff will meet in person with the caregivers and Veterans or call them to implement the standard consenting process that will be in compliance with VA Central IRB and Research & Development Committees at the 3 study sites. If a discharge date is not known at this time, study staff will call the caregiver on a weekly basis to check on the status of the veteran's discharge.

Once the Veteran and caregiver are enrolled in the study, baseline data will be collected over the phone. If the Veteran is an inpatient at the time of enrollment, baseline data will be collected after the Veteran is discharged. The research staff will ask the caregivers questions on the demographic data forms and survey questionnaires (stroke caregivers' depression, knowledge, perceived stress, burden, perception of positive aspects of caregiving, self-efficacy, health-related quality of life (HRQOL), and satisfaction with care).

The research staff member will also review the caregivers' Veterans CPRS record to document the Veterans' age, gender, race/ethnicity, category of facility (hospital, community living center, rehabilitation facility) from which the Veteran was discharged to home, length of hospital and/or post-stroke rehabilitation stay, date/location/type of the stroke, number of previous strokes, and healthcare use. The research staff member will document any information in the record related to the Veterans' discharge plans (i.e., treatments, medicines, patient and family education, case management, services).

The post-test assessments (stroke caregivers' depression, perceived stress, knowledge, burden, perception of positive aspects of caregiving, self-efficacy, health-related quality of life (HRQOL), and satisfaction with care) will be collected at approximately 11 weeks and approximately 19 weeks after the Veterans' discharge. A study team member at the main study site (Gainesville), who will be blinded to the group assignment of the caregivers, will telephone the caregivers to obtain the post-test assessments. The research staff will also review the Veterans' CPRS record and document the Veterans' healthcare utilization since their discharge to home. To minimize loss to follow-up, we will contact participants 24 hours before each post-test assessment to remind them of their scheduled appointment time. We will also mail postcards to enrolled caregivers who we cannot contact after 3 attempts to reduce attrition.

In the event that the RN conducting the intervention or the research personnel conducting the pre-and posttest assessments uncovers that the caregivers are experiencing unmanageable stress, but not severe stress, the research personnel will advise the caregivers to call their assigned VA primary care social workers and primary care clinicians (MD, ARNP, PA) of their Veterans' care team. The research personnel will also give the caregivers the phone number of the VA Caregiver Support Line and other referral sources as needed. If the research personnel assesses that the caregivers are in severe stress or crisis or if the research personnel uncovers that the Veteran has serious changes in his/her health, the research personnel will call the primary care provider/social worker of the Veteran's care team or the local emergency response system (9-1-1). In the event that any abuse or neglect is suspected, study personnel will follow established procedures by oversight agencies, including VHA as directed in the VA Handbook 1050.01, to contact the Office of Inspector General, Office of Investigation, as well as the IRB and the state of Florida Abuse Hotline.

Efforts to improve retention of participants: To improve the chances that participants will complete the project, we will conduct the 11-week and 19-week post-test assessments at times that are convenient to the caregivers.

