Our immediate, primary aim (#1) is to test the effect of the intervention on stroke caregivers' depressive symptoms at approximately 11 and 19 weeks after baseline data collection. Primary Hypothesis: Stroke caregivers who receive the intervention will have less depressive symptoms compared to stroke caregivers in usual care. We propose four secondary aims. Aim #2 is to test the effect of the intervention on stroke caregivers' knowledge, perceived stress, burden, perceptions of positive aspects of caregiving, self-efficacy, health-related quality of life (HRQOL), and satisfaction with care at approximately 11 and 19 weeks after baseline data collection. Aim #3 is to test the effect of the intervention on Veterans' outcomes: functional abilities and healthcare utilization (i.e., unintended hospital bed days of care, number of emergency room visits, number of unscheduled clinic visits) at approximately 11 and 19 weeks after baseline data collection. Aim #4 is to determine the budgetary impact for implementing the intervention. Aim #5 is to determine the facilitators, barriers, and best practices for implementing the intervention.

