Methods: We will conduct a two-group randomized controlled trial with repeated measures and use mixed methods to determine caregivers' perceptions of the intervention. We will enroll 240 stroke caregivers from 8 VA sites (North Florida/South Georgia Veterans Healthcare System, Miami VA Healthcare System, James A. Haley Veterans Hospital in Tampa, Michael E. Debakey VAMC in Houston, Hunter Holmes McGuire VAMC in Richmond, Central Arkansas Veterans Healthcare System, VA Tennessee Valley Healthcare System, and the VA Boston Healthcare System). Eligible caregivers will be interviewed, complete baseline measures, and then be randomized to two groups: 1) intervention group or 2) usual care group. A study team member will telephone caregivers at approximately 11 and 19 weeks after baseline to answer questions on instruments with established reliability and validity. The staff member will review the Veterans' VA Computerized Patient Record System health record to obtain information on the Veterans' healthcare utilization. We will determine the budgetary impact of the intervention by examining the cost data in the VA Managerial Cost Accounting System (MCAS) (formerly DSS) National Data Extracts (NDE) and Non-VA Medical Care files. Qualitative interviews will be conducted with selected caregivers to obtain in-depth perceptions of the value, facilitators, and barriers of the intervention. Throughout all phases of the project, we will collaborate with our VA partners (Office of Nursing Services, Office of Geriatrics and Extended Care).

Impact: This is the first known study to test a transition to home intervention combined with technology to improve the quality of caregiving and the recovery of Veterans. Other outcomes will be a state-of-the-art website and an evidence-based model (telephone, transition to home and online, training and caregiver-provider messaging) that can be transportable to other disease models.

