#### 5. **Specific Aims and Hypotheses:**

Our immediate, primary aim (#1): to test the effect of the intervention on stroke caregivers' depressive symptoms at approximately 11 and 19 weeks after baseline data collection. Hypothesis #1 (primary): Stroke caregivers who receive the intervention will have less depressive symptoms at approximately 11 and 19 weeks after baseline data collection compared to stroke caregivers in the usual care group.

We propose four secondary aims (#2-5):

Aim #2: to test the effect of the intervention on stroke caregivers' knowledge, perceived stress, burden, perceptions of positive aspects of caregiving, self-efficacy, health-related quality of life (HRQOL), and satisfaction with care at approximately 11 and 19 weeks after baseline data collection.

Hypotheses #2: (2a) Stroke caregivers who receive the intervention will have superior outcomes (i.e., greater knowledge, less stress, less burden, perceive more positive aspects of caregiving, greater self-efficacy, better health-related quality of life (HRQOL), and greater satisfaction with care) at approximately 11 and 19 weeks after baseline data collection than caregivers in the usual care group.

Aim #3: to test the effect of the intervention on Veterans' outcomes: Functional abilities and healthcare utilization (i.e., unintended hospital bed days of care, number of emergency room visits, number of unscheduled clinic visits) at approximately 11 and 19 weeks after baseline data collection.

Hypotheses #3: Veterans whose caregivers receive the intervention will have better functional abilities at approximately 11 and 19 weeks after baseline data collection and less healthcare utilization at 11 and 19 weeks after baseline data collection compared to Veterans whose caregivers are in the usual care group. Aim #4: to determine the budgetary impact for implementing the intervention.

Research question: What are the costs associated with the intervention and how do they compare to usual care?

Aim #5: to determine the facilitators, barriers, and best practices for implementing the intervention.

Research questions: What are the recommendations of VA leaders, policy makers, and clinicians for planning, developing, promoting, and evaluating and implementing the intervention in other sites? What are the caregivers' perceptions of the value, strengths, and weaknesses of the intervention, and what facilitators/barriers did they identify with the intervention?

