# Research Design & Methods (Aim #1, 2, 3)

**Design:** A two-group, randomized controlled trial with three assessment points (baseline, approximately 11 weeks, and approximately 19 weeks) will be conducted. The randomization will be stratified across study sites. Study Locations: We will recruit participants from a total of eight sites. We will have staff at three study sites in VISN8: NF/SG VHS in Gainesville, FL; James A. Haley Veterans Hospital in Tampa, FL; Bruce W. Carter Medical Center, in Miami, FL. Staff at these sites will also recruit from Michael E. Debakey VAMC in Houston, TX, Hunter Holmes McGuire VAMC in Richmond, VA, Central Arkansas Veterans Healthcare System, VA Tennessee Valley Healthcare System, and VA Boston Healthcare System via telephone and mail. All of the sites have large, in-patient hospitals, community living centers, and in-patient rehabilitation units; however, the Tampa site has a standardized, discharge planning process that involves Veteran education while the other sites have no discharge planning process. Thus, the usual/standard discharge planning care that Veterans receive at Tampa may be different than the care received by Veterans at the other sites. The research nurses will document the discharge planning care that the caregivers receive at all sites. In addition, research staff will review the Veterans' CPRS health records and describe the discharge planning care that is documented in the records. To address the issue of potential differences in usual care between study sites, and to aid in recruiting the necessary sample size, we will use a stratified, randomization procedure to achieve balanced group membership across the study sites. In our data analytic plan we will stratify by study sites in addition to controlling for baseline measurements.

Sample: We will recruit a total of 240 caregivers who will be randomized to an intervention or a usual care group (see randomization & power analysis in the data analysis section).

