**Eligibility Criteria:** Inclusion criteria: All caregivers of Veterans with a primary diagnosis of stroke are eligible for participation if they meet the following criteria: 1) are the primary caregiver and provide the majority of care for a Veteran who has a primary diagnosis of stroke (ICD10 codes for stroke: 160.0-169.998) and who has at least one activity of daily living (ADL) deficit or a new or worsening cognitive or physical functioning problem, 2) have internet and email access and ability, 3) are reachable by cell or home phone, 4) read English at the sixth grade reading level or better, 5) score 1 or greater on the Perceived Stress Scale and 6) plan to be ultimately discharged to home or have been discharged home within the preceding 4 months 7) agree to random assignment to the intervention or usual care group.

The research staff will use a checklist for caregiver enrollment to determine the caregivers' eligibility. The research staff will determine whether the Veteran has a primary diagnosis of stroke by reviewing the Veterans' CPRS health record and by conferring with the clinical staff. Caregiver status and responsibilities will be determined by caregiver self-report. We will determine the Veterans' ADL deficits by asking caregivers which ADL deficits their Veteran has on the Barthel Index. Reading level will be indicated by the Brief Health Literacy Level screening tool. Internet and email access and ability will be determined by caregiver self-report.

Exclusion criteria: We will exclude caregivers of Veterans who are terminally ill, who are prisoners, who fail to meet one or more of the inclusion criteria, and whose Veterans have a life expectancy of less than 6 months. We will also exclude professional caregivers who had no preexisting relationship to the Veteran. Caregivers who are enrolled in or have completed similar caregiver support programs will be excluded at PI discretion. Service use will be determined by reviewing the CPRS records. We will confer with the in-patient

staff and with our clinical team members (MDs, RNs) to approximate life expectancy. The study personnel will terminate the caregiver participation if the Veteran dies during the study.

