## Face-to-face recruitment (Gainesville, Miami, Tampa)

We will perform face-to-face recruitment for in-patient Veterans and Veterans returning for outpatient appointments at the Gainesville, Miami and Tampa sites. To recruit in-patient Veterans and Veterans returning to VA clinics for outpatient appointments, we will meet with the clinical staff in the VA settings that care for Veterans with strokes and describe our study. We will also notify VA clinicians of the study via email. Clinicians in the VA will ask Veterans with stroke who are receiving care on their units or facilities and/or their caregivers if they are interested in talking to a research staff member about the study. The VA clinicians who care for Veterans with a stroke are busy and often rotate shifts, so study Nurses will additionally review the VA's computerized record system (CPRS) to identify in-patient Veterans in order to assist the clinicians in locating potential participants. The study Nurses will review the minimum amount of information necessary to determine if the Veteran is admitted for new onset stroke. Once a Veteran is identified as having a new onset stroke, the study Nurse will notify a VA clinician involved in that Veteran's care either in person, by phone, or through encrypted e-mail. The clinician will then ask the Veteran and/ or caregiver if they are interested in talking to a research staff member about the study. If either the Veteran or caregiver is interested in the study, the study staff members will contact the caregiver and/or Veteran (using contact information found in CPRS or provided by the clinician) to arrange times to meet or talk with the caregiver and Veteran.

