## Outpatient Recruitment via Telephone (All Sites)

We will recruit Veterans that have been discharged home within the previous 4 months from all five settings. To recruit Veterans that have been discharged home within the last 4 months, we will develop a list of potential participants (including SSN and date of birth) by reviewing the VA Patient Care Encounter Package Dataset and the VA's Computerized Records System (CPRS) to identify Veterans at the 8 recruitment locations with a diagnosis of stroke based on ICD10 codes. We will mail letters of invitation and self-addressed, stamped, recruitment postcards with an opt-in/opt-out option to the Veteran or their next of kin.

A research staff member will then telephone the Veteran or their next of kin (i.e., those who returned the postcards with positive responses, those who did not return the postcards). The staff member will identify the Veteran's caregiver or confirm the next of kin is the Veteran's caregiver, explain the study and ask if there are questions. If the Veteran and caregiver are willing to participate, the staff member will confirm that the individuals meet all the other study eligibility criteria. The research staff will use a checklist for caregiver enrollment to determine the caregivers' eligibility (see inclusion/exclusion criteria section for procedures to determine caregivers' study eligibility). Once eligibility is confirmed, study personnel will mail Informed Consent Forms and HIPAA Authorization Forms, with a self-addressed stamped envelope so that the caregiver can mail it back to us. After caregivers and Veterans have had a chance to review the consent and HIPAA forms, the research staff will call the caregiver on the telephone to implement the standard consenting process that will be in compliance with VA Central IRB and Research & Development Committees at the study sites. We will also implement the consenting process, as described above, with the caregivers' Veterans. Once study personnel receive the signed forms, the original consents will be retained by PI in participant's subject file and a copy will be mailed to participants. Study documents for subjects from the Houston, Richmond, Central Arkansas. Tennessee Valley and Boston locations will be maintained by staff at the main study sites (Gainesville, Miami and Tampa).

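### The Data Collection section times both post-tests from the Veteran's discharge, but the aims and the analysis time them from baseline, which can come weeks later

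*Combined protocol and SAP*

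**What the plan says.** Under Data Collection, the post-test battery, which includes the depression score, is "collected at approximately 11 weeks and approximately 19 weeks after the Veterans' discharge". The same paragraph has staff review the Veteran's record for healthcare use since discharge home.

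Elsewhere the weeks run from baseline:

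- Abstract, primary aim: "stroke caregivers' depressive symptoms at approximately 11 and 19 weeks after baseline data collection".
- Abstract, Methods: a team member "will telephone caregivers at approximately 11 and 19 weeks after baseline".
- Section 5, Specific Aims and Hypotheses: "depressive symptoms at approximately 11 and 19 weeks after baseline data collection".
- Intervention Component #2: the optional calls for caregivers who stop the intervention are counted from baseline.
- Data Analysis, Hypotheses #1 to #3: both follow-up times, the primary contrast and the utilization periods are counted from baseline.

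The Design paragraph ("three assessment points (baseline, approximately 11 weeks, and approximately 19 weeks") and the Randomization section list the weeks without naming an origin.

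Four places bear on how far baseline can lie from discharge:

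- Eligibility Criteria admit caregivers whose Veterans "have been discharged home within the preceding 4 months".
- Outpatient Recruitment via Telephone targets Veterans "discharged home within the previous 4 months".
- Data Collection places baseline after discharge for Veterans enrolled as inpatients and sets no maximum interval.
- The Hypothesis #1 model includes time since discharge as a covariate.

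**The concern.** The sentence in question is in the section that tells staff when to collect the outcomes. It uses a different starting point from the analysis of those same outcomes, and nothing in the documents says which prevails.

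The primary contrast is the group difference at about 11 weeks after baseline. The model codes follow-up time only as 0 (11 weeks) or 1 (19 weeks), so it takes every first post-test to be at the same distance from baseline. If visits were scheduled from discharge, that distance would vary between caregivers with their lag, and for some the visit could not validly take place. The time-since-discharge covariate does not repair this. It enters additively, with no interaction with group, so it does not move a group difference measured at another time to 11 weeks after baseline.

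**Working it through.** The plan gives no figure to reproduce on this point. The check is calendar arithmetic on the stated visit times.

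**Inputs**

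- Visit times of 11 and 19 weeks: Data Collection (from discharge); Abstract, Specific Aims and Data Analysis (from baseline).
- Entry limit of 4 months after discharge: Eligibility Criteria and Outpatient Recruitment via Telephone. In weeks: 4 × 365.25 / 12 / 7 = 17.4.
- Order of events: the Randomization section places assignment after the baseline assessments.
- Lag L = weeks from discharge to baseline. The documents do not give its distribution, so the results below are shown over a range.

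**Formula**

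A visit T weeks after discharge falls T − L weeks after baseline.

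| L (weeks) | First post-test, 11 − L | Second post-test, 19 − L |
|---|---|---|
| 0 | 11 | 19 |
| 2 | 9 | 17 |
| 4 | 7 | 15 |
| 8 | 3 | 11 |
| 11 | 0 | 8 |
| 17.4 (4 months) | −6.4 | 1.6 |

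**Reading the table**

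- The clocks agree only at L = 0.
- At L = 8 the second discharge-timed visit falls where the analysis places the first.
- Above L = 11 the first post-test comes before baseline, and so before randomization. The entry window runs 17.4 − 11 = 6.4 weeks beyond that point.

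**How large L can be**

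The 4 months limits eligibility and recruitment; it is not a stated limit on when baseline is taken. Intervention Component #2 has the in-home sessions begin within four months of discharge. Baseline and the telephone session come before those, so for intervention caregivers who start on that schedule baseline falls earlier than four months. That still leaves room for lags above 11 weeks.

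**Healthcare utilization**

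Hypothesis #3 analyses use from baseline to about 11 and 19 weeks after baseline. A record review done at discharge-timed visits would end 11 − L and 19 − L weeks after baseline, so it falls short of each endpoint by 11 − (11 − L) = L weeks. At L = 4 it stops at weeks 7 and 15. Because it starts at discharge, it would also include L weeks of use before baseline.

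**The case against.** The strongest reply is that this is one stray phrase, probably left over, in an otherwise consistent plan. The Abstract's Methods summary gives baseline as the origin of the calls, and so does the rule for caregivers who stop the intervention. The assessment points in the Design paragraph are most naturally read as counted from baseline. Staff facing a long lag would find that the first visit had to precede baseline, and would notice the error. For Veterans enrolled as inpatients, the lag may be short and the clocks nearly the same.

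Much of this stands: the intended origin can be inferred, and the documents do not show that staff would follow the discharge clock. But the Methods text is a summary, and the rule for those who stop covers only that subgroup. The Data Collection sentence is the one that sets the timing for both arms. At lags of a few weeks the schedule is feasible, so the error would not reveal itself.

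Three stronger readings are not supported:

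- A reader might infer that a known fraction of the intervention is lost, by dividing 11 − L by 11. The analysis fixes an assessment time; it does not assume 11 weeks of intervention. The documents give one or two telephone sessions and 8 in-home sessions, but neither their frequency nor their total duration. Lost exposure, and hence dilution, at short lags cannot be computed.
- A reader might infer bias toward one arm. The lag is fixed before assignment, so there is no reason to expect it to differ systematically between arms.
- A reader might infer that a since-discharge record already covers the analysed utilization period. At discharge-timed visits it would not, as shown above.

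**Conclusion.** The inconsistency is real and should be corrected. As written, the Data Collection rule for the primary outcome conflicts with the aims and the analysis. If followed, it would place both post-tests L weeks too early on the analysis clock, and for L above 11 weeks the first would fall before randomization. Those scores would not estimate the intervention effect at about 11 weeks after baseline.

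The size of the shift for a given L is exact. How many caregivers it would affect is unknown, because the distribution of L is not given. That L varies is the plan's own premise, since its entry window allows a range of lags and its model adjusts for time since discharge. The conclusion does not depend on any assumption about session timing, and no estimate of lost intervention exposure is made.

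**What to change.** In Data Collection, change the origin of both post-tests from discharge to baseline data collection, for all caregivers in both arms. This matches the Abstract, Specific Aims, the rule for caregivers who stop the intervention, and Data Analysis.

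In the same paragraph, time the record review from baseline as well, and count utilization from baseline to about 11 and 19 weeks after it, as the Hypothesis #3 analysis requires.

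Naming baseline as the origin in the Design paragraph and the Randomization section would be optional tidying.

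The cost is a one-phrase correction for the post-tests and a matching change for the record review. No visits, instruments or data sources are added.

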## Recruitment and enrollment:

The study will be open to all eligible caregivers. The caregivers will be recruited from 8 settings (North Florida/South Georgia Veterans Healthcare System, Miami VA Healthcare System, James A. Haley Veterans Hospital in Tampa, Michael E. DeBakey VAMC in Houston, Hunter Holmes McGuire VAMC in Richmond, Central Arkansas Veterans Healthcare System, VA Tennessee Valley Healthcare System, and VA Boston Healthcare System). We will also recruit from each facility's associated community-based outpatient clinics. Although we will recruit from the Houston, Richmond, Central Arkansas, Tennessee Valley and Boston VA Systems, all study procedures will be performed by staff at the North Florida/South Georgia, Tampa and Miami locations (i.e., no personnel at the Houston, Richmond, Arkansas, Tennessee or Boston facilities will be engaged in research). Staff at the main study sites (North Florida/South Georgia, Miami and Tampa) will be responsible for maintaining study records for participants recruited from Houston, Richmond, Arkansas, Tennessee and Boston.

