We will maintain records of "exact correspondence" of the caregiver and nurse communications on the messaging center. We will also collect data on the time spent or minutes that the caregivers and study nurse interact via the messaging center. This data will allow us to monitor participant adherence. To minimize loss to follow-up, if necessary, we will contact participants 24 hours before scheduled data collections/sessions to remind them of their session. We will also mail reminder postcards to enrolled caregivers that we are unable to contact after 3 attempts to reduce attrition.

If after starting, a caregiver is unable or unwilling to continue with the intervention they will be offered the opportunity to discontinue the intervention but remain in the study for data collection phone calls. These phone calls will occur approximately 11 and 19 weeks after baseline data collection. To be eligible to complete these optional data collection phone calls, the caregiver must have completed at least one phone or messaging center intervention session.

Usual Care Group: The caregivers' Veterans will receive usual or standard care. The caregivers will receive the standard information and discharge planning that is provided to all stroke caregivers. There will be no changes in the care the Veterans normally receive or in the information and discharge planning that the caregivers normally receive.

**Fidelity Considerations:** We will develop standardized manuals and protocols. This manual will provide step-by-step guidelines on recruiting/enrolling participants, implementing the informed consent process, in conducting the transition-to-home and in-home sessions and implementing the data collection procedures. We will provide extensive training to all of our team members. The PI and one staff member will periodically visit (minimally once a year) the Tampa and Miami study sites and observe the research nurses conducting the transition-to-home session. Feedback will be provided as needed.

Similar to our previous projects, we will have regular conference calls with our team members at the three study sites (Gainesville, Miami and Tampa). In these meetings, team members will describe how they are

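### The abuse-reporting instruction names only Florida's hotline at state level, although five of the eight recruitment sites are outside Florida

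*Combined protocol and SAP*

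**What the plan says.** The instruction is in the Data Collection section, at the end of the paragraph on what staff do when they uncover distress or danger. If abuse or neglect of any kind is suspected, "study personnel will follow established procedures by oversight agencies, including VHA as directed in the VA Handbook 1050.01", and contact the inspector general's investigations office "as well as the IRB and the state of Florida Abuse Hotline". The sentence does not say whether the suspected victim is the Veteran or the caregiver.

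The preceding sentence deals with a caregiver in severe stress or crisis, or a serious change in the Veteran's health. It directs staff to the Veteran's care team or to local 9-1-1. It is not presented as a route for reporting abuse.

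The Study Locations text under Research Design & Methods lists eight sites. Gainesville, Tampa and Miami are in Florida and have study staff. Those staff also recruit from Houston, Richmond, "Central Arkansas Veterans Healthcare System, VA Tennessee Valley Healthcare System, and VA Boston Healthcare System via telephone and mail". Recruitment and enrollment adds that "all study procedures will be performed by staff at the North Florida/South Georgia, Tampa and Miami locations" and that "no personnel at the Houston, Richmond, Arkansas, Tennessee or Boston facilities will be engaged in research".

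A manual is mentioned twice. Data Collection states: "Research personnel will follow a step-by-step study procedure manual to collect the data". Fidelity Considerations describes the contents: "This manual will provide step-by-step guidelines on recruiting/enrolling participants, implementing the informed consent process, in conducting the transition-to-home and in-home sessions", followed by the data collection procedures. The manual is not among the documents.

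**The concern.** The protocol foresees suspected abuse or neglect and prescribes a response, but the state-level part of that response names one state while recruitment reaches well beyond it. The person who forms the suspicion will be an interviewer or nurse at a Florida-based location, in contact by telephone or messaging with a household that may be in Texas or Massachusetts. No research staff at the remote facility are there to supply a local contact.

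The Veterans are dependent by design. Eligibility requires a deficit in daily activities or a new or worsening cognitive or physical problem, and some Veterans enter through a legally authorized representative because their decision-making capacity is reduced. What is at stake is whether staff have a clear instruction at the moment it is needed. If the text is followed as written, a report about someone in Houston or Boston goes to no named agency in that person's own state.

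**Working it through.** No formula and no planned figure bear on this point. The check is a count of sites and a comparison of the reporting sentence with the site plan.

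**Sites by state**, from Study Locations and Recruitment and enrollment. Boston is taken to be in Massachusetts, and Central Arkansas and Tennessee Valley are placed by their names.

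| State | Sites | State contact named |
|---|---|---|
| Florida | Gainesville, Tampa, Miami | Yes |
| Texas | Houston | No |
| Virginia | Richmond | No |
| Arkansas | Central Arkansas | No |
| Tennessee | Tennessee Valley | No |
| Massachusetts | Boston | No |

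- Sites outside Florida: 8 − 3 = 5, and 5/8 = 62.5% of sites.
- States without a named contact: 6 − 1 = 5, and 5/6 = 83.3% of states.

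These fractions count facilities and states. They do not count participants, because enrolment by site is not given and a facility's location is not a participant's residence.

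**Reach of each route in the reporting paragraph:**

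1. Oversight-agency and VHA procedures: general wording, applies at all eight sites.
2. Inspector general: federal, applies at all eight sites.
3. IRB: applies at all eight sites.
4. State agency: Florida only.
5. Care team or local 9-1-1: available wherever the Veteran lives, but triggered by crisis or serious health change, not by suspected abuse as such.

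Routes 1 to 3 fit the eight-site design. Route 4, the only explicit state instruction, fits three of the eight sites.

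**Consistency with the rest of the text.** Other sentences also look as if they were not adjusted to eight sites. Outpatient Recruitment via Telephone refers to five settings and, one sentence later, to eight locations. Data Analysis contrasts Tampa with Miami/Gainesville when it describes results conditional on site. It is a fair inference, but only an inference, that the Florida phrase was also not revisited. The conclusion does not depend on it.

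**The case against.** The strongest reply is that the operative duty is general. Staff follow the procedures of oversight agencies, VHA is given as one example, and that wording could take in other states' agencies. The federal and IRB routes reach every site. A contact list is manual-level detail, and the unseen manual may already contain one: its stated contents do not name abuse reporting, but the data collection procedures they include could cover it. Naming the state where the reporting staff work is also coherent, and the documents contain no rule on which state has jurisdiction.

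Most of this stands, and it is why the point ranks low. It also disposes of three stronger readings that a reader might infer:

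- *Participants outside Florida have no reporting route.* They have the inspector general, IRB and VHA routes, and local emergency help in a crisis.
- *The plan breaches a reporting duty, or Florida is the wrong contact.* That depends on state law and on the cited VA handbook, neither of which is in the documents.
- *The manual omits other states.* The manual is not available, so its silence cannot be assumed.

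The reply does not alter the one state instruction that the protocol does give. A general clause leaves staff to work out the state step for themselves, while the only explicit direction points to Florida.

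**Conclusion.** The point holds as a low-severity participant-safety matter. The protocol states a specific rule, and its state-level part does not match a design in which five of eight sites lie outside Florida and are run remotely from Florida-based locations.

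The site count is certain from the text. The consequence rests on one assumption: that at least some participants recruited through those five sites live outside Florida. That is very likely, but residence is not stated.

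A reader might take the 62.5% or 83.3% as the share of participants at risk. The documents do not support that, because they give neither enrolment by site nor an expected number of reports. The estimand, sample size, power and analysis are unaffected.

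**What to change.** Keep every existing contact and add the affected person's state. In the Data Collection sentence, the ending could become: *as well as the IRB, the state of Florida Abuse Hotline, and the abuse hotline or adult protective service of the state where the person suspected of being abused or neglected (Veteran or caregiver) lives.*

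Two features of this wording matter. The Florida contact stays unconditional, so a clear instruction is not replaced by a test of when Florida reporting applies. The added contact follows the residence of the person at risk, not the Veteran's alone, because the trigger covers any abuse or neglect, and eligibility does not require the caregiver to live with the Veteran. Keying on residence also covers people who live in a different state from the recruiting facility.

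List the state contacts in the study manual, starting with Texas, Virginia, Arkansas, Tennessee and Massachusetts.

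The cost is one phrase in the protocol and at least five manual entries to compile and keep current. Design, sample size and analysis do not change.
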